Study Title: An investigation into the feasibility of incorporating an exercise rehabilitation programme for people with intermittent claudication into an already established Cardiac Rehabilitation service

Protocol

Overview

This study will look at the feasibility of combining patients with peripheral artery disease (PAD) and coronary artery disease (CAD) into one supervised exercise programme (SEP). The study will assess the effects of the intervention quantitatively, and also investigate the patient experience qualitatively by applying a mixed methods design (figure 1). The initial phase of the research will quantitatively analyse pre and post-intervention outcomes, followed by qualitative investigation into the thoughts and concerns about the intervention. The rationale for this mixed methods approach is that it provides strengths that offset the weaknesses of both qualitative and quantitative methods when used in isolation (Creswell & Plano Clarke, 2007). Also in clinical settings such as in the NHS, exploring the views and experiences of the service users to gain greater understanding has been shown to improve service provision and subsequently patient uptake (Risom et al., 2013).

[figure not shown]

Figure 1: This diagram shows the mixed methods approach of the research study, with the qualitative element following on from the quantitative measurement of the intervention outcomes. The results of each arm will be merged to show the overall effectiveness of the intervention.

Recruitment Strategy:

Intervention group:

Participants for the combined SEP will be recruited from a local NHS Vascular Service at Salford Royal NHS Foundation Trust (SRFT). They will be identified by the vascular specialist teams (surgeons, nurses and podiatrists) and asked if they wish to take part in the study. The participants will be asked during the face-to-face consultation with their specialist, or a telephone consultation. This will give participants 1-2 week period to consider enrolling in the research programme. Participation will be on a voluntary basis. Simultaneously, an agematched group of coronary artery disease (CAD) patients will be recruited to the combined programme to assess the impact of combined SEP on CAD patients. These participants will be identified by the Cardiac Rehabilitation Specialist Nurses at SRFT upon referral to the CR SEP and will have a similar 1-2 week period to decide about enrolling.

Control group or "standard care" group:

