A control group will also be recruited. This group will be made of PAD patients only and will take place at an established SEP at Central Manchester University Hospitals. The use of a SEP has been chosen as the control group or "standard care" group, even though most patients are unable to receive the standard care in the UK. Other research in this area has had an "exercise advice only" group as control (Cheetham et al., 2004) however, it has been established that SEPs are better than "exercise advice only" as a treatment option (Bendermacher, Willigendal, Teijink and Prins, 2009). Therefore it would be unethical for some participants to be missing out on the recommended SEP treatment.

The CAD patient's outcomes will be compared to the National Audit of Cardiac Rehabilitation (NACR) as it is outside of the scope of this investigation to have a CAD only control group. The NACR data is compiled annually and records all of the outcome measures that are included in this study. The recent year's audit results will be used for comparison.

Informed Consent

In order to gain informed consent from prospective participants, the content and layout will verbally be given to prospective participants, along with an easy-to-read leaflet/letter with full description of the study (see Patient Information Sheet in supporting documents). To avoid any risk of coercion, it will be explicitly stated that they have the right to withdraw from the study at any point, and that no present or future treatment will be affected by enrolling or not enrolling on the study. All documents will be available in large print if required.

Sample size:

The sample size of this investigation has been guided by a study by Evans et al., (2010) which investigated the suitability of combining two different patient groups (heart failure and chronic obstructive pulmonary disorder) into one rehabilitation programme. The authors of this study established that 17 participants were required in each group to reach significance level.

There will be 3 participant groups in this study: The stand-alone PAD group; the combined PAD group, and the combined CR group (see figure 2). In order to generate sufficient data 34

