patients will be recruited to each group with an aim to achieve 17 completers from each group. This is due to an expectation of high dropout rate for both PAD and CAD programmes seen at a national level (NACR, 2016; Shalhoub et al., 2009). The total recruited will therefore be 102 subjects, to gain 51 completers totally (17 per group).

[figure not shown]

Figure 2 - Flowchart of study. This shows the outline of the 12 week study with the 3 groups involved

Inclusion and Exclusion Criteria

General criteria

As part of this study participants will be required to wear an accelerometer on the first week and last week of the 12 week study. The accelerometer will be kept in place by a medical dressing (e.g. Tegederm). People with an existing skin condition such as psoriasis or eczema that would be affected by the application of a medical dressing will be excluded from the study.

All participants must be able to start the incremental shuttle walk test (walking speed of 1.8kph, 1.1 mph). If they are unable to walk at this pace they will be excluded from the study.

All participants must be able to engage in the exercises prescribed in the programme (see Supervised Exercise Programme outline below).

No participant will be excluded due to age or gender.

Inclusion Criteria – PAD patients:

All patients recruited will have had a recent diagnosis (0 – 12 months) of PAD made by either a vascular surgeon, vascular specialist nurse or specialist podiatrist.

Exclusion criteria – PAD patients:

Any patient who has had previous intervention for PAD e.g. balloon angioplasty, stent, bypass or medication, or who have previously completed an SEP will be excluded from the study. This is due to the possibility of previous interventions having an impact on patient perceptions.

Participants who are on medication for PAD (e.g. naftidrofuryl oxalate) will also be excluded from the study as this can increase symptom management and improve functional capacity.

Any PAD patient who also has a diagnosis of other cardiovascular conditions such as CAD or stroke, or chronic heart failure will be excluded from this study, as the investigation is looking at the specific improvements in PAD, not CAD gains.

Inclusion Criteria – CAD patients:

All patients recruited to the CR group will have had a recent diagnosis (0-12 months) of CAD (angina, myocardial infarction (MI), or coronary artery bypass graft (CABG) or valve surgery).

Exclusion criteria – CAD patients:

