Upon completion of the 12-week supervised exercise programme, participants will be invited to attend focus groups to explore their thoughts and concerns about the intervention (Figure 2). Themes will be constructed from the data to give insight into the experiences of the different participant groups. As participation is important for rehabilitation departments, it is essential to include the participants' perspective in the evaluation of the treatment programme.

Data Analysis:

Quantitative data:

The outcome data will be tested to see if it is normally distributed or not. SPSS software will then be used to assess for any statistically significant differences between the groups. Within groups and between group differences in exercise capacity will be analysed using a factorial ANOVA to compare the difference in the levels of improvement between groups. Wilcoxon tests will be used to analyse the questionnaire data.

The CAD group will also be compared to the National Audit of Cardiac Rehabilitation (NACR) data to assess the impact on the CAD group performance against expected national levels. The effect sizes will be calculated using the Cohen's *d* so that the results can be compared to other studies.

Qualitative Data:

The analysis will be influenced by Braun & Clarke's (2006) six phases of thematic analysis as described in Table 2.

Phase	Description of the process

1. Familiarizing yourself with your	Transcribing data (if necessary), reading and re-reading
data:	the data, noting down initial ideas.
2. Generating initial codes:	Coding interesting features of the data in a systematic
	fashion across the entire data set, collating data relevant
	to each code.
3. Searching for themes:	Collating codes into potential themes, gathering all data
	relevant to each potential theme.
4. Reviewing themes:	Checking if the themes work in relation to the coded
	extracts (Level 1) and the entire data set (Level 2),
	generating a thematic 'map' of the analysis.
5. Defining and naming themes:	Ongoing analysis to refine the specifics of each theme, and
	the overall story the analysis tells, generating clear
	definitions and names for each theme.
6. Producing the report:	The final opportunity for analysis. Selection of vivid,
	compelling extract examples, final analysis of selected
	extracts, relating back of the analysis to the research
	question and literature, producing a scholarly report of
	the analysis.

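### The CAD group's only between-group comparator is unrestricted national audit data, which can benchmark the service but cannot isolate the effect of combining CAD and PAD patients

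*Protocol*

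**What the plan says.** **Purpose of the CAD group.** Under Recruitment Strategy (Intervention group), the protocol says that an "agematched group of coronary artery disease (CAD) patients will be recruited to the combined programme to assess the impact of combined SEP" in these patients. They are "identified by the Cardiac Rehabilitation Specialist Nurses at SRFT upon referral to the CR SEP and will have a similar 1-2 week period" in which to choose whether to join.

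**Comparator.** Under Control group, the protocol explains that "it is outside of the scope of this investigation to have a CAD only control group". The recent year's NACR "audit results will be used for comparison". The support offered is that NACR is compiled annually and records the study's outcome measures. The study's own control group is PAD patients only, at a different hospital.

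**Analysis.** Protocol, Data Analysis (Quantitative data), and the SAP section of the same name carry identical text: "The CAD group will also be compared to the National Audit of Cardiac Rehabilitation (NACR) data", in order to judge the group's performance relative to the national expectation. No subset of NACR, standardisation, adjustment or analysis set is named.

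**Who is in the CAD group.** "All patients recruited to the CR group will have had a recent diagnosis (0-12 months) of CAD". "All participants must be able to start the incremental shuttle walk test". Patients with previously diagnosed PAD are excluded because PAD could hide improvement from cardiac rehabilitation, and patients with unstable CAD are excluded as unsuitable for structured exercise. Each group recruits 34 "with an aim to achieve 17 completers from each group", completion being 8 or more of 12 sessions.

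**Use of the results.** Both documents close by saying that the quantitative and focus-group results together will inform conclusions on how effective the treatment options are.

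**The concern.** The stated reason for enrolling CAD patients is to learn whether training alongside PAD patients affects them. That needs a contrast between CAD patients in a combined programme and similar CAD patients in a CAD-only programme. The plan's only between-group contrast for CAD is with a national audit whose population neither document describes.

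The reason given for using NACR concerns measurement: the same outcomes are recorded. It does not address whether the same kind of patient was measured. If the CAD group did better or worse than NACR, or about the same, a reader could take this as evidence that combining helps, harms or is neutral. Each result could equally reflect which patients were enrolled, where they were treated or, if the analysis sets differ, who completed. Services considering combined programmes would rely on that reading.

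**Working it through.** No figure in the plan is disputed, so this is mainly a check of what the design can identify.

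**1. The plan's own numbers.** 17 completers ÷ 34 recruits = 0.50, so the recruitment target implies 50% dropout. 3 × 34 = 102 recruits and 3 × 17 = 51 completers. These reproduce the protocol's totals.

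**2. The available contrasts.**

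| Group | Condition | Programme | Source |
|---|---|---|---|
| Stand-alone PAD | PAD | PAD only | Central Manchester |
| Combined PAD | PAD | Combined | SRFT |
| Combined CR | CAD | Combined | SRFT |
| NACR | Audit population, not described | Not described | National |

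Only one study group has CAD. The factorial ANOVA therefore contains no comparison of combined with CAD-only rehabilitation, and NACR is the only between-group CAD comparator.

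**3. What the NACR difference contains.** Let D be the mean change in the study's CAD group minus the mean change in NACR. Then

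D = effect of combining + site difference + case-mix and selection difference + completion difference (if the sets differ) + chance.

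The plan yields D. It gives no second CAD contrast and no adjustment with which to separate the terms. Because all study CAD patients are in the combined programme and come through one trust, the first two terms always occur together.

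**4. Are the populations aligned by design?** Setting the sections side by side:

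- *PAD.* Previously diagnosed PAD is excluded from the CAD group, with the reason that it could hide gains. No matching restriction on NACR is stated. On the protocol's own reasoning, if the audit includes such patients, this one factor would favour the study group.
- *Diagnosis window, walking ability, decision to enrol.* All three are study criteria. No corresponding NACR restriction is stated, and the documents do not say how these factors relate to gain.
- *Age.* The CAD group is called age-matched in the passage describing recruitment alongside the PAD patients. Matching to NACR is not stated.
- *Completion.* Outcomes are repeated when the programme is completed, but the NACR comparison does not say whether all recruits or completers are used on either side.

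One factor has an inferable direction under a condition that cannot be checked, and the others have none. The net direction and size are therefore unknown.

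**5. Precision, separate from bias.** Assume a 95% t interval for the CAD mean change, with the NACR mean treated as fixed. The half-width in SD units of change is t(0.975, n−1)/√n. For n = 17 this is 2.120/4.123 = 0.51 SD. For n = 34 it is 2.035/5.831 = 0.35 SD. Even without bias, a finding of no difference would be compatible with a sizeable shortfall, so an interval should be reported.

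**The case against.** The strongest case against is that the plan claims less than the concern supposes.

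- The analysis text frames the NACR comparison as performance relative to national expectation, which is benchmark language. The causal wording is in the recruitment section, as a reason for enrolling the group. *This stands, and it limits the point to what the comparison may be used for.*
- The closing statements name neither NACR nor CAD. They can be read as being about stand-alone versus combined exercise for PAD patients, who have their own control group. *This also stands.* A reader might infer that the plan commits itself to attributing an NACR difference to combining. The documents do not say so. They also contain nothing to prevent it.
- NACR is not the only evidence on CAD patients: within-group change and focus groups are planned too. *True, but neither isolates the effect of combining.*
- The lack of a CAD control is disclosed, and this is a feasibility study. *Disclosing that there is no control is not the same as saying what the substitute can show.* No new arm is being asked for.
- Some criteria may not distinguish the group from NACR. CAD patients are identified on referral to cardiac rehabilitation, CAD exercise follows national guidance, and unstable CAD is excluded as a contraindication that other programmes may also apply. *This stands: a case-mix difference is possible but not shown.*

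A reader might also infer that the comparison is materially biased, or try to calculate a false-positive rate for it. The documents do not support either step. They give no NACR case mix and no outcome offset, and they plan no named test against NACR, so any such rate would only restate the assumption put in.

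**Conclusion.** The point holds in a limited form. NACR is the only between-group comparator for the CAD group, the comparison is planned without restriction or standardisation, and the CAD group is selected by stated criteria and comes through one trust. The comparison is a reasonable service benchmark, but it cannot isolate the effect of combining the two patient groups. That conclusion follows from the structure of the design and does not depend on the bias being large.

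The size and direction of any case-mix bias cannot be obtained from the documents and may be small. The only criterion that the protocol itself links to the amount of gain is the PAD exclusion. The half-width of about 0.51 SD with 17 completers describes sampling precision under the stated assumptions and is not an estimate of bias.

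It would go too far to say that the NACR comparison is wrong or should be dropped, or that the CAD results will mislead. What is missing is alignment of the comparison where possible and a stated limit on its interpretation.

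**What to change.** **Protocol and SAP, Data Analysis (Quantitative data).** Specify that the CAD group's baseline-to-12-week change will be compared with NACR figures restricted or standardised to the same age, sex, diagnosis and completion status where NACR provides them. State whether all recruits or completers are analysed, and use the same set on both sides. Report the difference with a 95% CI and label it a descriptive benchmark. If the strata are unavailable, mark the comparison as unadjusted.

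**Closing statement in both documents.** Add that the CAD-versus-NACR difference, or the lack of one, will not be attributed to combining the groups.

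**Cost.** Wording changes and modest analysis work, with no new recruits, groups or measurements. There are two downsides. NACR strata may be incomplete, in which case the label and the interpretive limit have to carry the correction. The conclusion about CAD patients also becomes more modest: performance alongside national figures, not the effect of combining.

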Date: 16/08/2017

Study Title: An investigation into the feasibility of incorporating an exercise rehabilitation programme for people with intermittent claudication into an already established Cardiac Rehabilitation service

Data Analysis:

Quantitative data:

The outcome data will be tested to see if it is normally distributed or not. SPSS software will then be used to assess for any statistically significant differences between the groups. Within groups and between group differences in exercise capacity will be analysed using a factorial ANOVA to compare the difference in the levels of improvement between groups. Wilcoxon tests will be used to analyse the questionnaire data.

The CAD group will also be compared to the National Audit of Cardiac Rehabilitation (NACR) data to assess the impact on the CAD group performance against expected national levels. The effect sizes will be calculated using the Cohen's *d* so that the results can be compared to other studies.

Qualitative Data:

The analysis will be influenced by Braun & Clarke's (2006) six phases of thematic analysis as described in Table 2.

Phase	Description of the process
1. Familiarizing yourself with your	Transcribing data (if necessary), reading and re-reading
data:	the data, noting down initial ideas.
2. Generating initial codes:	Coding interesting features of the data in a systematic
	fashion across the entire data set, collating data relevant
	to each code.
3. Searching for themes:	Collating codes into potential themes, gathering all data
	relevant to each potential theme.

4. Reviewing themes:	Checking if the themes work in relation to the coded extracts (Level 1) and the entire data set (Level 2),
5. Defining and naming themes:	generating a thematic 'map' of the analysis. Ongoing analysis to refine the specifics of each theme, and
5. Defining and naming themes.	the overall story the analysis tells, generating clear definitions and names for each theme.
6. Producing the report:	The final opportunity for analysis. Selection of vivid, compelling extract examples, final analysis of selected extracts, relating back of the analysis to the research question and literature, producing a scholarly report of the analysis.

Table 1 This table outlines the steps taken in the thematic analysis of the focus group data. Taken from: Braun & Clarke, (2006) Using thematic analysis in psychology. Qualitative Research in Psychology. 3: pp77-101

The results of both the quantitative data analysis and the thematic analysis from the focus groups will then be used to draw conclusions about the effectiveness of the treatment options.
